6.3.2 Transvaginal Ultrasound

Transvaginal ultrasound (TVU) will be performed by the investigator, sub-investigator or designated trained member of the staff at the Screening Visit to determine whether there are any abnormalities of the ovaries, whether the uterus and cervix are present, and whether there are any physical issues that would exclude the subject from participation in the study. In addition, TVU will be performed to measure endometrial thickness and to investigate the presence of any abnormal morphological findings. Follow-up TVU will be

conducted during the Week 12/Early Termination Visit, and any clinically significant changes from baseline will be noted.

6.3.3 Endometrial Biopsy

Endometrial biopsy will be performed per the provided standard collection method. Samples are to be fixed and stored using directions supplied by the centralized laboratory. The investigator shall do his/her best to obtain endometrial tissue for analysis. The Investigator must record whether tissue was obtained, and send the tissue obtained to the centralized laboratory to be processed.

At the centralized laboratory, a single pathologist will assess the slides from the endometrial biopsies obtained at Screening (per the standardized criteria for determining hyperplasia, as detailed in *Blaustein's Pathology of the Female Genital Tract* (Kurman RJ, 2011) as well as any biopsies obtained if a subject experiences vaginal bleeding while on study drug. Three independent pathologists (from different institutions with independent fiduciary and organizational reporting), blinded to subject's treatment group and to each other's readings, will assess the endometrial biopsies obtained at the Week 12/Early Termination Visit. The concurrence of two of the three pathologists will be accepted as the final diagnosis. If there is no agreement among the three pathologists, the most severe pathologic diagnosis (i.e., atypical hyperplasia > complex hyperplasia > simple hyperplasia > benign endometrium) would be used as the final diagnosis. If hyperplasia is diagnosed by the single safety reader for a subject who has bled while on study drug, this diagnosis be maintained for the efficacy evaluation and the slides become part of the slide set given to the two other pathologists for reading.

Per the draft FDA guidance on estrogen and estrogen/progestin drug products to treat vasomotor symptoms and vulvar and vaginal atrophy symptoms (US Dept. Health and Human Services, 2003), the set of slides distributed to each of these pathologists for the end-of-study pathology review will incorporate control slides representing a randomly selected 10% of the screening normal slides and all slides from subjects excluded for the diagnosis of hyperplasia or cancer to insure quality control.

6.3.4 Adverse Events

6.3.4.1 Definitions of Adverse Events

The investigator is responsible for reporting all adverse events (AEs) that are observed or reported during the study, regardless of their relationship to study drug or their clinical significance.

An AE is defined as any untoward medical occurrence in a subject enrolled into this study regardless of its causal relationship to study drug. An AE can, therefore, be any unfavorable and unintended sign (including an abnormal laboratory finding, for example), symptom, or disease temporarily associated with the use of a medicinal (investigational) product, whether or not considered related to the medicinal (investigational) product. Subjects will be instructed to contact the investigator at any time, after the subject gives informed consent until the end of study, if any symptoms develop.

Note that, for the purpose of this protocol, the following circumstances – with or without associated adverse event/reaction - should be included the eCRF:

- Overdose, abuse, misuse
- Off-label use
- Medication error

A treatment-emergent AE (TEAE) is defined as any event not present before exposure to study drug or any event already present that worsens in either intensity or frequency after exposure to study drug.

A serious AE (SAE) is defined as any event that:

- Results in death;
- Is immediately life-threatening;
- Requires inpatient hospitalization or prolongation of existing hospitalization;
- Results in persistent or significant disability/incapacity; or
- Is a congenital anomaly/birth defect

- Is a medically significant event

Medically significant events are defined as important medical events that may not result in death, be life-threatening, or require hospitalization but may be considered SAEs when, based upon appropriate medical judgment, they may jeopardize the subject or may require medical or surgical intervention to prevent one of the outcomes listed in this definition. Examples of such medical events include allergic bronchospasm requiring intensive treatment in an emergency room or at home, blood dyscrasias or convulsions that do not result in inpatient hospitalization, or the development of drug dependency or drug abuse.

Disability is defined as a substantial disruption of a person's ability to conduct normal life functions.

A **life-threatening adverse event** is one that places the subject, in the view of the investigator, at immediate risk of death from the event as it occurred. It does not include an event that, had it occurred in a more severe form, might have caused death.

An **unexpected adverse event** is any adverse drug event, the nature, specificity or severity of which is not consistent with the applicable product information (e.g. Investigator's brochure for an unauthorized investigational product or summary of product characteristics for an authorized product).

Enter only one event as the reason for the SAE on the SAE form. Other non-serious events which did not directly result in the SAE should be detailed in the description section on the SAE form and listed separately as AEs if necessary.

ANY SERIOUS ADVERSE EVENT MUST BE REPORTED IMMEDIATELY (WITHIN 24 HOURS) BY THE STUDY SITE VIA EMAIL OR FAX TO [REDACTED]
[REDACTED] PHARMACOVIGILANCE GROUP USING THE SAE FORM PROVIDED.
ENTER THE SUBJECT'S AVAILABLE INFORMATION INTO THE eCRF WITHIN 48 HOURS.

A SAE occurring during the study must be reported to the [REDACTED] Pharmacovigilance Group. Any such SAE due to any cause, whether or not related to the study drug, must be reported within 24 hours of occurrence or when the Investigator becomes aware of the event. SAEs occurring more than 4 weeks of stopping the treatment

and considered related to the study drug will be communicated. Notification can be made with the SAE reporting form by using the dedicated fax line or by scanning and emailing to the safety mailbox for the [REDACTED] Pharmacovigilance Group:

[REDACTED] Pharmacovigilance Fax Number: [REDACTED]

[REDACTED] Pharmacovigilance Email: [REDACTED]

The event must also be recorded on the standard AE eCRF. Preliminary reports of SAEs must be followed by detailed descriptions later on, including clear and anonymized photocopies of hospital case reports, consultant reports, autopsy reports, and other documents when requested and applicable. SAE reports must be made whether or not the Investigator considers the event to be related to the investigational drug.

Appropriate remedial measures should be taken to treat the SAE, and the response should be recorded. Clinical, laboratory, and diagnostic measures should be employed as needed in order to determine the etiology of the problem. The Investigator must report all additional follow-up SAE information to the [REDACTED] Pharmacovigilance Group within 24 hours of awareness of the information. All SAEs will be followed until the Investigator and Sponsor agree the event is satisfactorily resolved.

Any SAE that is not resolved by the end of the study or upon discontinuation of the subject's participation in the study is to be followed until it either resolves, stabilizes, returns to baseline values (if a baseline value is available), or is shown to not be attributable to the study drug or procedures.

Reports relating to the subject's subsequent medical course following a SAE must be submitted to [REDACTED] until the event has subsided or, in case of permanent impairment, it stabilizes and the overall clinical outcome has been ascertained.

All SAEs will be reported to the institutional review board (IRB)/independent ethics committee (IEC) periodically for SAEs that meet reporting guidelines or at a frequency determined by the IRB/IEC, at the end of the study, or per local institutional guidelines.

All suspected unexpected serious adverse reactions (SUSARs) will be reported in an expedited manner to [REDACTED] per the ICH Guideline for GCP and IRB/IEC

by the investigators and to all relevant regulatory authorities [REDACTED]. A SUSAR is a SAE that is both related to the study drug (Relationship = Related) **and** unexpected (not previously described in the Investigator's Brochure). Expectedness will be judged by the Sponsor's medical monitor. It is therefore essential that all SAEs are reported within the 24-hour guideline so that the expectedness determination can be made. All SUSARs require immediate attention and expedited reporting to relevant regulatory authorities.

[REDACTED] is to ensure that all relevant information about **fatal or life threatening** SUSARs are appropriately recorded and reported to the concerned Regulatory Authority and to the concerned IRB(s)/IEC(s) within 7 calendar days of the date of first report [REDACTED]. Follow-up information is to be subsequently communicated to the relevant Regulatory Authority within an additional 8 calendar days.

All other SUSARs are to be reported to the Regulatory Authority and to the IRB(s)/IEC(s) concerned as soon as possible within a maximum of 15 calendar days of first knowledge by [REDACTED].

The medical monitor/Sponsor or designee must also inform all investigators studying the investigational medicinal product about SUSARs and ensure that IRBs/IECs have been notified.

For reported death of a subject, the investigator shall supply the Sponsor, [REDACTED] and/or the IRB(s)/IEC(s) with additional information requested on an expedited basis.

The following events are **not** considered SAEs:

- A visit to the emergency room or other hospital department lasting less than 24 hours that does not result in admission (unless considered an "important medical event" or a life-threatening event).
- Elective surgery planned before signing consent.
- Hospitalization which is due solely to a planned study visit and without prolongation.
- Routine health assessment requiring admission for baseline/trending health status (e.g., routine colonoscopy).

- Medical/surgical admission for purpose other than remedying ill health state that was planned before study entry. Appropriate documentation is required in these cases.
- Admission encountered for another life circumstance that carries no bearing on health status and requires no medical/surgical intervention (e.g., lack of housing, economic inadequacy, caregiver respite, family circumstances, administrative reasons).
- An overnight stay in the hospital that is only due to transportation, organization, or accommodation problems and without medical background.

These events will be reported in the eCRF and in the subject record.

6.3.4.2 Eliciting and Documenting Adverse Events

Adverse events will be assessed from the time the subject signs the informed consent form until exit from the study.

Events that occur prior to signing the informed consent form will be entered as medical history; AEs that have an onset after signing the informed consent will be entered on the AE form.

Subjects will be questioned and observed for evidence of AEs, whether or not related to study drug. For any pre-existing condition or abnormal laboratory finding that changes in severity after dosing, the change should be recorded as an AE. New abnormal laboratory findings that are considered clinically significant by the investigator are considered AEs.

All AEs will be collected through the Follow-up Visit (i.e. the Week 16 phone call, 4 weeks after discontinuation of study drug). Adverse event details are to be documented, including start and stop dates, whether continuous or intermittent, severity, any intervention utilized to correct the event, outcome of the event, and the relationship to the study drug.

All AEs determined by the investigator to be related to study drug must be followed until resolution, until they are considered stable, or for at least 30 days after discontinuation of study drug, whichever occurs first.

Adverse events should be classified following the Medical Dictionary for Regulatory Activities (MedDRA). Safety/PV will use the MedDRA medical dictionary to map the AE/SAE verbatim terms to specific system organ classes (SOC) and preferred terms.

Note that, for the purpose of this protocol, the following circumstances (with or without associated adverse event/reaction) should be included in the data base and will be submitted to the Sponsor, being managed in the same way and time as adverse events/reactions: any overdose (with or without associated AEs), abuse, misuse, off-label use, or medication error.

The causal relation between the investigational product and the AE will be assessed by the investigator using the following assessment criteria:

UNRELATED: This category applies to those AEs that are clearly and incontrovertibly due to extraneous causes (disease, environment, etc).

UNLIKELY: This category applies to those AEs that are judged to be unrelated to the study drug, but for which no extraneous cause may be found. An AE may be considered unlikely to be related to study drug if or when it meets 2 of the following criteria: (1) it does not follow a reasonable temporal sequence from administration of the study drug; (2) it could readily have been produced by the patient's clinical state, environmental or toxic factors, or other modes of therapy administered to the patient; (3) it does not follow a known pattern of response to the study drug; or (4) it does not reappear or worsen when the drug is re-administered.

POSSIBLY: This category applies to those AEs for which a connection with the study drug administration appears unlikely but cannot be ruled out with certainty. An AE may be considered possibly related if or when it meets 2 of the following criteria: (1) it follows a reasonable temporal sequence from administration of the drug; (2) it could not readily have been produced by the patient's clinical state, environmental or toxic factors, or other modes of therapy administered to the patient; or (3) it follows a known pattern of response to the study drug.

PROBABLY: This category applies to those AEs that the investigator feels with a high degree of certainty are related to the study drug. An AE may be considered probably related if or when it meets 3 of the following criteria: (1) it follows a reasonable temporal sequence from administration of the drug; (2) it could not be reasonably explained by the known characteristics of the patient's clinical state, environmental or toxic factors, or other modes of therapy administered to the patient; (3) it disappears or decreases on cessation or reduction in dose (note that there are exceptions when an AE does not disappear upon discontinuation of the drug, yet drug-relatedness clearly exists; for example, as in bone marrow depression, fixed drug eruptions, or tardive dyskinesia); or (4) it follows a known pattern of response to the study drug.

DEFINITELY: This category applies to those AEs that the investigator feels are incontrovertibly related to study drug. An AE may be assigned an attribution of definitely related if or when it meets all of the following criteria: (1) it follows a reasonable temporal sequence from administration of the drug; (2) it could not be reasonably explained by the known characteristics of the patient's clinical state, environmental or toxic factors, or other modes of therapy administered to the patient; (3) it disappears or decreases on cessation or reduction in dose and recurs with re-exposure to drug (if rechallenge occurs); and (4) it follows a known pattern of response to the study drug.

Possibly, probably and definitely will fit the characterization of “related AE.” Unlikely and unrelated will fit the characterization of “not related AE.”

6.3.4.3 Reporting Adverse Events

All AEs reported or observed during the study will be recorded on the AE page in the eCRF. Information to be collected includes subject code, age, site, drug treatment and dose (if available), event term, time of onset, investigator-specified assessment of severity and relationship to study drug, time of resolution of the event, seriousness, any required treatment or evaluations, outcome, improvement of the AE after suspension/withdrawal of study drug, time of study (at screening, during treatment, or at follow-up) and action taken with the study drug. Adverse events resulting from concurrent illnesses, reactions to concurrent illnesses, reactions to concurrent medications, or progression of disease states must also be reported. All AEs will be followed to adequate resolution. MedDRA will be used to code all AEs.

Any medical condition that is present at the time that the subject is screened but does not deteriorate should not be reported as an AE. However, if it deteriorates at any time during the study, it should be recorded as an AE.

Any AE that meets SAE criteria (Section 6.3.4.1) must be reported to [REDACTED] [REDACTED] immediately (i.e., within 24 hours) after the time site personnel first learn about the event. The contact information in Section 6.3.4.1 is to be used for SAE reporting.

6.3.4.4 Assessment of Severity

The severity, or intensity, of an AE refers to the extent to which an AE affects the subject’s daily activities. The intensity of the AE will be rated as mild, moderate, or severe using the following criteria:

MILD: An event that is easily tolerated by the patient, causing minimal discomfort and not interfering with everyday activities.

MODERATE: An event that is sufficiently discomforting to interfere with normal everyday activities.

SEVERE: An event that considerably restricts or prevents normal everyday activities.

Changes in the severity of an AE should be documented to allow an assessment of the duration of the event at each level of intensity to be performed. Adverse events

characterized as intermittent do not require documentation of onset and duration of each episode.

6.3.4.5 Assessment of Causality

The investigator's assessment of an AE's relationship to study drug is part of the documentation process, but it is not a factor in determining what is or is not reported in the study. If there is any doubt as to whether a clinical observation is an AE, the event should be reported. The relationship or association of the test article in causing or contributing to the AE will be characterized using the following classification and criteria:

Not Related AEs = those with no relationship with the study drug; other factor(s) (including subject's clinical state or other therapy administered) may be causative.

Related AEs = those with a reasonable possibility that the event was caused by the study drug (i.e. a time relationship exists, the AE is a known effect of the study drug or class of drugs, or the AE resolves/abates upon discontinuation of study drug), and other possible causative factor(s) may exist.

6.3.4.6 Follow-Up of Subjects Reporting Adverse Events

All AEs must be reported in detail on the appropriate page in the eCRF and followed to satisfactory resolution, until the investigator deems the event to be chronic or not clinically significant, or until the subject is considered to be stable.

6.4 Evaluation of Acceptability

At the Week 12/Early Termination Visit, the subject will be asked to rate the acceptability of the therapy received over the completed study period. The acceptability is defined as the subject's perceptions of the ease in the method of administration and cleanliness of the product. The subject will be asked to rate the acceptability of the therapy as: excellent, good, acceptable, or unacceptable.

6.5 Laboratory Analyses

Any abnormal laboratory test results (hematology, clinical chemistry, or urinalysis, as described in Section 6.3.1), including those that worsen from baseline, felt to be clinically

significant in the medical and scientific judgment of the investigator are to be recorded as AEs or SAEs.

However, any clinically significant safety assessments that are associated with the underlying disease, unless judged by the investigator to be more severe than expected for the subject's condition, are **not** to be reported as AEs or SAEs.

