Vulvovaginal atrophy is a natural consequence of the progressive estrogen deficiency that occurs in menopause. Epidemiological data have indicated that about 50% of otherwise healthy women over 60 years of age experience symptoms related to urogenital atrophy such as vaginal dryness, dyspareunia, burning, itching, as well as urinary complaints or infections of the lower urinary tract. As these alterations frequently affect the quality of life of postmenopausal women, it is important for doctors to detect their presence and offer treatment options.

Estrogen therapy is the most effective treatment of moderate to severe symptoms of vulvar and vaginal atrophy. Scientific societies agree that when estrogen therapy is considered for treatment of vaginal atrophy, local treatment is advised (The 2007 Hormone Therapy Position Statement of the North American Menopause Society, 2007). One advantage of local treatment with estrogen is avoidance of first-pass liver metabolism, making it possible to use lower doses of estrogen compared with oral therapy; the local route also minimize systemic adverse effects.

The primary risks of taking an estrogen product after menopause is that it can cause or exacerbate certain types of tumors, such as breast or endometrium. Taking low dose estrogens vaginally decreases the risk of the occurrence of these tumors, as a consequence of the very low doses employed that permit a local vaginal effect while the potential of absorption is minimized. It has been shown that lower doses of vaginal estrogen therapy than previously used, even with less frequent administration, often yield satisfactory results. The lowest effective dose of estrogen consistent with treatment goals, benefits, and risks for the individual woman should be the therapeutic goal (The 2012 Hormone Therapy Position Statement of the North American Menopause Society, 2012).

Estriol (E3) is one of the most important estrogens produced in the human body, along with 17β -estradiol (E2) and estrone (E1). Estriol is normally produced in the liver by irreversible transformation of estradiol and estrone. This process is considered to be a metabolic detoxification mechanism, by which potent estrogens are transformed into less active metabolites such as estriol. Also, estriol is produced in significant amounts during pregnancy as it is synthesized by the placenta. In all instances, there is no conversion from estriol to estradiol or estrone.

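### Protocol 6.5 bars disease-associated findings no worse than expected from AE and SAE reporting, although 6.3.4.1 to 6.3.4.3 require it for new findings, deterioration and SAEs

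*Protocol*

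**What the plan says.** Protocol 6.5 (Laboratory Analyses) has two paragraphs. The first sends abnormal laboratory results that the investigator thinks clinically significant, including those that worsen from baseline, to the AE or SAE record. The second makes an exception: "any clinically significant safety assessments that are associated with the underlying disease, unless judged by the investigator to be more severe than expected". Severity is weighed against what the investigator would expect in that woman. Findings under the exception are not "to be reported as AEs or SAEs".

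The adverse event sections set these duties:

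- **6.3.4.1:** the investigator's duty covers "reporting all adverse events (AEs) that are observed or reported during the study, regardless of their relationship to study drug or their clinical significance". On serious events: "Any such SAE due to any cause, whether or not related to the study drug, must be reported within 24 hours".
- **6.3.4.2:** "New abnormal laboratory findings that are considered clinically significant by the investigator are considered AEs". A pre-existing condition or laboratory abnormality whose severity changes after dosing is also recorded as an AE.
- **6.3.4.3:** a condition present at screening is not an AE while it does not deteriorate, and becomes one if it does. AEs that result from, among other things, concurrent illness "or progression of disease states must also be reported".

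None of these three sections mentions an exception for the underlying disease, and 6.5 does not refer to them on this point.

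**The concern.** The protocol gives two opposite instructions for the same finding. An investigator who follows the second paragraph of 6.5 literally leaves out events that 6.3.4.1 to 6.3.4.3 require. That includes serious events, because the exception names SAEs as well as AEs.

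Safety and tolerability is a secondary objective (Protocol 2.2), and SAP 6.4.1 bases the safety assessment on AE incidence. If about 25 sites in five countries resolve the conflict differently, the AE counts will partly reflect which section each site read.

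For SAEs the issue is compliance, whatever the counts. Section 6.3.4.1 asks for all SAEs within 24 hours so that the sponsor's medical monitor can judge expectedness. A case withheld under 6.5 never reaches that person.

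**Working it through.** No figure in the plan bears on this point, so there is nothing to recompute. The check sets the rules side by side for each kind of clinically significant finding that an investigator associates with the underlying disease.

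| Finding | Under 6.3.4.1 to 6.3.4.3 | Under 6.5, second paragraph | Result |
|---|---|---|---|
| Condition present at screening, not deteriorated | Not an AE (6.3.4.3) | Not reported | Agree |
| More severe than expected | AE if new or worsened | Exception does not apply; recorded | Agree |
| New laboratory finding, no more severe than expected | AE (6.3.4.2) | Not reported | Conflict |
| Pre-existing condition or finding, worse after dosing but no worse than expected | AE (6.3.4.2, 6.3.4.3) | Not reported | Conflict |
| Meets an SAE criterion, no more severe than expected | Report within 24 hours (6.3.4.1) | Not reported | Conflict |

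The conflict therefore covers three cases: new findings, deterioration judged no worse than expected, and SAEs.

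**Does another passage settle it?**

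- Section 6.3.4.1 lists events that are not SAEs. Findings associated with the underlying disease are not on the list, and even the listed events go into the eCRF.
- Section 6.3.4.5 says that relationship to study drug does not decide what is reported, and that doubtful observations should be reported. That default deals with doubt about whether something is an AE. It does not lift an explicit instruction in 6.5 not to report.
- No section states an order of precedence.

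**Can a finding fall in the conflict zone?** The protocol does not define the underlying disease. If it means vulvovaginal atrophy, the Introduction's list of related symptoms ends "as well as urinary complaints or infections of the lower urinary tract", and 6.3.1 schedules urinalysis with microbiology at Screening and Week 12. Exclusion criterion 10 keeps out women with signs and symptoms suggesting genital or urinary infection that needs treatment at the start, so a clinically significant positive result at Week 12 could well be new. It would be an AE under 6.3.4.2. If the investigator linked it to atrophy and thought it no worse than expected, 6.5 would keep it out. This shows that the overlap is possible, but says nothing about how often it occurs.

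**How many events?** The documents give no rate of disease-associated findings and no share that investigators would attribute to the disease, so no count can be derived.

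**The case against.** The best defence is that 6.5 states a rule and then a specific exception to it, and that an exception in a laboratory section has a short reach. Few blood or urine results are likely to be ascribed to vulvovaginal atrophy. The urinary example is strained: the symptoms scored under 6.2.3.1 include dysuria but not infection, and the investigator must both attribute a new infection to atrophy and find it no worse than expected. The SAE rule is prominent, and 6.3.4.5 leans towards reporting. Laboratory data also survive without an AE entry: SAP 6.4.5 summarises continuous parameters, lists categorical ones and provides shift tables.

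Most of this stands as a limit on size. It does not remove the contradiction. Nothing in 6.3.4.1 to 6.3.4.3 yields to 6.5, and a laboratory table does not replace a required AE or SAE report.

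A reader might infer more than the documents support:

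- **Bias between arms.** It is tempting to argue that atrophy-linked findings persist more on placebo and so are left out more often there. Persistence without deterioration is not an AE under 6.3.4.3 either, so 6.5 removes nothing in that case. For new or worsened findings, the documents contain nothing to show that omissions would differ by arm.
- **Local effects of the gel written off as disease.** The exception speaks of safety assessments, which is looser than laboratory tests, but it sits in a section on laboratory results. Symptoms and signs are scored separately at Weeks 3 and 12 (6.2.3), and tolerability is evaluated at Weeks 3, 8, 12 and 16 (Table 1, footnote f). Those data do not depend on 6.5.
- **Disease progression as an AE in itself.** The sentence in 6.3.4.3 has as its subject adverse events that result from progression. It does not turn progression into an AE; the deterioration rule in the same section carries the point.

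**Conclusion.** The contradiction is real and limited. Section 6.5 conflicts with 6.3.4.1 on SAEs, with 6.3.4.2 on new clinically significant laboratory findings and post-dose changes in severity, and with 6.3.4.3 on deterioration of a condition present at screening. It does not conflict for stable pre-existing conditions, and it is not a blanket exemption, since findings judged more severe than expected remain reportable.

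The size cannot be estimated from the documents. It is probably small if the underlying disease means vulvovaginal atrophy, which is an assumption because the term is undefined. No distortion of the comparison between arms is shown. The point should still be corrected, because a site that follows 6.5 as written would withhold events that other sections require, and one withheld SAE would breach the 24-hour rule.

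**What to change.** Reconcile 6.5 with 6.3.4.1 to 6.3.4.3 so that one rule applies:

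1. Delete the reference to SAEs from the exception in the second paragraph of 6.5, so that it cannot override the any-cause, 24-hour rule.
2. State there that 6.3.4.1 to 6.3.4.3 govern, so that the exception covers only pre-existing findings that have not worsened. This matches what 6.3.4.3 already says of stable conditions, and how the underlying disease is defined then no longer decides whether a new, worsened or serious finding is reported.
3. Send sites a short note with the same wording.

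The cost is one sentence in the protocol, the site note and a few more recorded AEs. The AE definitions and tables in the SAP need no change.
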